### 6.1.2 DAILY HOME SWABS - DAYS 1-8

Parents will be asked to take daily nasal swabs from their child/young person at home, in the week following vaccination, from Day 1 until Day 8 post vaccination. The nasal swab, which looks like a large cotton bud, will be passed into the nostril and moved around for a minute. Parents will be provided with eight test kits, full instructions and Royal-Mail approved postage kits (for Category B specimens) and prepaid envelopes for each child, for posting back to PHE through the normal Royal Mail network.

Parents will be shown the process by their study nurse at the vaccination visit. Parents will receive a daily reminder text/email to take and post the samples. In the event of a missed swab, families will be asked to take the swabs as planned the next day. The final Day 8 swab can be collected up to 24 hours late i.e. on Day 9.

Adverse event information will be collected on a daily basis, using the form parents are asked to complete when they return the daily swabs to Public Health England.

### 6.1.3 VISIT 2 - DAY 28 (WINDOW DAY 21 TO DAY 42) FOLLOWING VACCINATION

- Confirm continued consent with parent/ guardian and note continuation on GP notes and CRF (if consent withdrawn, complete a withdrawal form documenting this).
- Obtain interim history, specifically any serious adverse events, serious reactions, and visits to hospital – report SAEs according to section 7 below.
- Take nasal swab (same as initial swab)
- Collect oral fluid sample
- Collect a blood sample (up to 25ml). Participants will be offered local anaesthetic cream (to be applied 30mins prior to venepuncture) to minimise discomfort.
- 2nd dose of LAIV were indicated:

Children who meet DoH criteria for specified 'clinical risk categories' (Table 1) and are under 9 years of age and have not received prior seasonal influenza vaccination will also be offered a second dose of LAIV. We expect very few children to meet this criteria, as most would have received prior influenza vaccination. However, there is a duty of care to our participants and we are therefore including provision for a second dose in this protocol.

**Table 1: Clinical risk categories requiring a second dose of LAIV in vaccine-naïve children under age 9 yrs:**

Chronic respiratory disease	
 
• Asthma requiring continuous or repeated use of inhaled or systemic steroids or with previous exacerbations requiring hospital admission.
 
• Chronic obstructive pulmonary disease (COPD) including chronic bronchitis and emphysema; bronchiectasis, cystic fibrosis, interstitial lung fibrosis, pneumoconiosis and bronchopulmonary dysplasia (BPD).
 
• Children who have previously been admitted to hospital for lower respiratory tract disease.
 

Chronic heart disease	Congenital heart disease, hypertension with cardiac complications, chronic heart failure.
Chronic kidney disease	Chronic kidney disease at stage 3, 4 or 5, chronic kidney failure, nephrotic syndrome, kidney transplantation.
Chronic liver disease	Cirrhosis, biliary atresia, chronic hepatitis
Chronic neurological disease	Stroke, transient ischaemic attack (TIA). Conditions in which respiratory function may be compromised due to neurological disease (e.g. polio syndrome sufferers). Clinicians should consider on an individual basis the clinical needs of patients including individuals with cerebral palsy, multiple sclerosis and related or

	similar conditions; or hereditary and degenerative disease of the nervous system or muscles; or severe neurological or severe learning disability.
Diabetes	Type 1 diabetes, type 2 diabetes requiring insulin or oral hypoglycaemic drugs, diet controlled diabetes.
Immunosuppression	
Immunosuppression due to disease or treatment. Patients undergoing chemotherapy leading to immunosuppression. Asplenia or splenic dysfunction.
 
HIV infection at all stages.
 
Individuals treated with or likely to be treated with systemic steroids for more than a month at a dose greater than 20mg prednisolone per day (any age); or for children under 20kg, a dose greater than 1mg per kg per day.
 
It is difficult to define at what level of immunosuppression a patient could be considered to be at a greater risk of the serious consequences of influenza and should be offered influenza vaccination. This decision is best made on an individual basis and left to the patient's clinician.
 
Some immunocompromised patients may have a suboptimal immunological response to the vaccine.
 
NB: LAIV is not contraindicated for use in individuals with asymptomatic HIV infection; or individuals who are receiving topical/inhaled corticosteroids or low-dose systemic corticosteroids or those receiving corticosteroids as replacement therapy, e.g. for adrenal insufficiency.

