##### 4.2.2 EXCLUSION CRITERIA

1. **Contraindications to LAIV** (notwithstanding allergy to egg protein), which include:
  - a. Hypersensitivity to the active ingredients, gelatin or gentamicin (a possible trace residue)
  - b. Previous systemic allergic reaction to LAIV
  - c. Previous allergic reaction to an influenza vaccine (not LAIV) is a relative contra-indication, which must be discussed with the CI to confirm patient suitability

- d. Children/adolescents who are clinically immunodeficient due to conditions or immunosuppressive therapy such as: acute and chronic leukaemias; lymphoma; symptomatic HIV infection; cellular immune deficiencies; and high-dose corticosteroids\*.

\***High-dose steroids** is defined as a treatment course for at least one month, equivalent to a dose *greater than* 20mg prednisolone per day (any age), or for children under 20kg, a dose *greater than* 1mg/kg/day.

NB: LAIV is not contraindicated for use in individuals with asymptomatic HIV infection; or individuals who are receiving topical/inhaled/low-dose oral systemic corticosteroids or those receiving corticosteroids as replacement therapy, e.g. for adrenal insufficiency.

- e. Children / adolescents younger than 18 years of age receiving salicylate therapy because of the association of Reye's syndrome with salicylates and wild-type influenza infection.
- f. Pregnancy (determined by history). Where this cannot be confirmed, a urine pregnancy test will be performed.

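### Table 1 lists immunosuppressed groups for a second LAIV dose that section 4.2.2 treats as contraindicated, and Visit 2 requires no contraindication re-check before that dose

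*Combined protocol and SAP*

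**What the plan says.** Section 6.1.3 sets the second-dose rule for children in a Table 1 category: those "under 9 years of age and have not received prior seasonal influenza vaccination will also be offered a second dose of LAIV". The table is headed "Clinical risk categories requiring a second dose of LAIV in vaccine-naïve children under age 9 yrs". Its Immunosuppression row opens with "Immunosuppression due to disease or treatment. Patients undergoing chemotherapy leading to immunosuppression" and goes on to HIV and prolonged high-dose steroids.

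Section 4.2.2, item 1d, lists clinical immunodeficiency among the contraindications to LAIV, with examples and a definition of high-dose steroids.

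At Visit 1 (section 6.1.1) the team verifies the inclusion and exclusion criteria, and the section 6 schedule marks a medical assessment at that visit only. The Visit 2 list in 6.1.3 has no matching item. Its nearest entry is "Obtain interim history, specifically any serious adverse events, serious reactions, and visits to hospital". Section 4.3 allows withdrawal for ineligibility that arises during the study or was overlooked at screening, but as something that may be done.

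**The concern.** The second-dose rule and the contraindication list use overlapping definitions and give opposite answers. Staff working from 6.1.3 and its table would find a chemotherapy patient, or a child on prolonged high-dose steroids, named as someone who needs the dose. Nothing at that point sends them to 4.2.2. This is a written rule that points the wrong way on the safety of a live vaccine, which is more than a missing detail. As drafted, catching the problem depends on someone linking the interim history to an exclusion list that the Visit 2 procedures do not mention.

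**Working it through.** No statistical figure is involved, so the check sets the texts side by side and then asks who could be affected.

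**1. Overlap of the Immunosuppression row with 4.2.2, item 1d**

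| Table 1 row | 4.2.2, item 1d | Conflict |
|---|---|---|
| Immunosuppression from disease or treatment, and chemotherapy | "Children/adolescents who are clinically immunodeficient due to conditions or immunosuppressive therapy such as", followed by examples including leukaemias and lymphoma | Yes, once the child is clinically immunodeficient. Chemotherapy is not named in 1d but falls under immunosuppressive therapy |
| "HIV infection at all stages" | Symptomatic HIV is contraindicated; asymptomatic HIV is expressly not | Yes for symptomatic HIV, no for asymptomatic |
| "treated with or likely to be treated with systemic steroids for more than a month at a dose greater than 20mg", or above 1 mg/kg/day under 20 kg | Same dose thresholds, course of at least one month | Yes for a course that has run more than a month, since that is also at least one month. Item 1d has no wording about likely future treatment, so planned courses are not counted here |
| Asplenia or splenic dysfunction | Not named | None shown |

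**2. Does the row resolve the conflict itself?** It leaves a decision to the patient's clinician, introduced by "It is difficult to define at what level of immunosuppression a patient could be considered to be at a greater risk". That sentence is about who is at enough risk from influenza to be offered vaccination. It does not address who can safely receive a live vaccine. The closing note says who is *not* contraindicated (asymptomatic HIV; topical, inhaled, low-dose or replacement steroids). It suggests that others in the row are contraindicated, but does not say so.

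**3. Who can reach the conflict?**
- Enrolment starts at age 6 and the second dose stops at 9, so the child is aged 6 to 8.
- The child must have had no previous seasonal influenza vaccine.
- The child passed the 4.2.2 check at Visit 1, so must either become contraindicated before Visit 2 (day 21 to 42) or have been missed at screening.
- Section 6.1.3 expects very few second doses, and the study enrols up to 30. The contraindicated subset is smaller still, and the documents give no rate for it.

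**4. Is any check required before dose 2?** The Visit 2 list covers consent, interim history, samples and the dose where indicated. The interim history would probably bring out a new leukaemia, chemotherapy or symptomatic HIV through the question on hospital visits. It does not ask about new medication, so a steroid course managed outside hospital could go unmentioned. Section 4.3 gives a power to withdraw a child, without requiring anyone to look for new ineligibility.

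**5. Effect on the results.** The day 1 to 8 shedding swabs precede any second dose, and the Visit 2 list puts sampling ahead of it. The section 9.1 outcomes are unaffected if that order is followed.

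**The case against.** The strongest reply is that the conflict is almost empty. The 4.2.2 list is headed as contraindications to the product and is not limited to the first dose, so it naturally governs any dose. Visit 1 screening removes these children before Table 1 can apply. Other text points the same way:

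- Section 5.2 ties administration to the product characteristics.
- The synopsis makes the second dose subject to Department of Health and PHE guidelines.
- The Visit 2 bullet evidently means the dose is given where indicated, and 6.1.3 speaks of an offer.
- Section 4.3 allows withdrawal in the child's best interests.
- Section 10.3 leaves the clinician free to depart from protocol treatment.

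Most of this stands, and it lowers the risk. None of it is a required check before dose 2, and none of it corrects the table.

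A reader might infer that the study plans to give live vaccine to immunosuppressed children. The documents do not support that, because 4.2.2 bars them at entry.

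A reader might also infer that serious-event reporting lapses after dose 2, because 7.1.1 and 7.3.2 give 28 days without naming a dose. Counted from dose 1, a dose on day 21 would have 28 − 21 = 7 days left, and a dose on day 28 or later none. The documents do not support this as a defect either. Counting from each dose is the natural reading, the adverse-reaction definition in 7.1 covers any dose, and the reporting flowchart is not visible in the copy reviewed.

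**Conclusion.** The conflict in the text is real and minor. Table 1 marks for a second dose several groups that 4.2.2, item 1d, lists as contraindicated, and the Visit 2 procedures require no re-check. It can matter only for a vaccine-naive child aged 6 to 8 who is newly contraindicated or was missed at screening. Very few children could be affected, possibly none, and the analysis is untouched. The conclusion rests on two assumptions: that the Visit 2 list states the required steps in full, and that the guidelines and product information it relies on, which are not reproduced, are not themselves set out as a pre-dose check. The serious-event window is at most an optional wording clarification.

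**What to change.** Add *unless contraindicated under 4.2.2* to the second-dose sentence in 6.1.3 and to the Table 1 heading. Add a line to the Visit 2 list, before the second dose, requiring 4.2.2 to be checked again, including current medication. Checking the whole list would also pick up a systemic allergic reaction to the first dose (item 1b).

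The cost is a few words of protocol text and a brief check for the very few children offered a second dose, with no extra visit and no change to sampling or analysis. If the text is being amended anyway, 7.1.1 and 7.3.2 could say that the 28 days run from each dose. For second-dose children that would take reporting to between day 49 (21 + 28) and day 70 (42 + 28), so the participant duration of about one month in 6.5 would need a matching note.

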## 6.2 CONSENT

We will endeavour to provide the Patient Information Leaflets prior to visit to hospital, but this may not always be possible. Patients may therefore be consented (according to Good Clinical Practice) without a requirement for a 'cooling-off' period following receipt of the study information leaflets, **where this is specifically requested by the family**. In this case, at least 30 minutes will be allowed for participants and their carers to read the patient information provided and consider the contents.

The reasons for this were highlighted in the PPI discussions during the development of the previous SNIFFLE protocols and include:

- Many families travel significant distances to specialist clinics, often requiring the child to miss school and their parents/carers to miss work. In previous studies by this group, for example SNIFFLE-1, families frequently requested vaccination at the same time as their routine outpatient appointment, to avoid having to make a second trip to hospital.
- The vaccine to be administered in this study is part of the routine UK National Immunisation Schedule. The study allows children to participate in this programme in a safe environment, utilising a vaccine delivery route (intranasal) which minimises discomfort to the child.
- The proposed consent process has been trialled successfully in the SNIFFLE-2 and -3 studies and the Flu-shed study, with positive feedback from both eligible young people and their families.

## 6.3 COLLECTION AND POSTING OF SAMPLES

### 6.3.1 COLLECTING SAMPLES

#### **Baseline Nasal swab:**

*Will be collected by research team staff and stored at -20 °C until processing at Imperial College London.*

#### **Nasal swabs:**

Parents will be asked to take daily nasal swabs from their child according to the schedule described above. Parents will be provided with eight test kits, each with prepaid returns to the testing laboratory (PHE), for their child and instructions as per appendix 1, as well as being shown the process by their study nurse at the vaccination visit. This will involve putting a swab, which looks like a large cotton bud, into each nostril and moving it around for up to a minute.

#### **Oral fluid samples:**

The first oral fluid sample will be collected by the nurse at the day 0 appointment, the second at Visit 2. The procedure involves passing a foam tipped swab across the teeth and gum line for around a minute in an action similar to brushing teeth.

#### **Blood samples**

Blood sampling will be performed by Trust-approved phlebotomy staff or the research team in accordance with local protocol. No more than two attempts at venepuncture will be made at any one time. Anaesthetic cream (e.g. EMLA or Ametop) will be offered for use at the intended sampling site to minimise discomfort.

The following blood samples (total volume 25ml, maximum 2.5ml/kg body weight) will be collected, prior to and 3-6 weeks after LAIV vaccination:

- 5ml into a tube for collection of clotted blood (for serum studies)
- 18ml into Lithium Heparin tubes for processing in PBMCs (for CMI)
- 2ml into a PAXgene RNA tube (for global assessment of host response by whole blood transcriptomics)

### 6.3.2 LABELLING SAMPLES

All samples will be labelled with the participant's unique identification number. Participants will be assigned a 2 digit number (01 etc.). Numbers will be used sequentially in order of enrolment to the study. Labels will also identify the protocol (i.e. FluSHED-2) such that all labels per child will be uniform e.g. FLU2-01. Nurses and or parents will complete the date sample taken alongside this prior to posting, so a swab label should say e.g. FLU-01 Day1 7.10.18, FLU-02 Day2 8.10.18 etc.

### 6.3.3 POSTING SAMPLES

Appropriate prepaid postage packs will be provided to parents to return **nasal swabs** on the day each is taken. Samples will be sent by Royal Mail to the Influenza Laboratory, Public Health England (PHE Colindale). **Oral fluid samples** will be sent directly to PHE by the research team.

All samples to be sent to PHE will be placed into a NOAX green topped tube containing an absorbent strip and then placed in an approved transport box (along with Sample Postage and Receipt Form CTD014). The box is then placed into a postage bag showing the “UN3373 biological substance, category B” identification diamond sticker, and either dropped at a post office or into a post box for delivery to the Influenza Laboratory, PHE Colindale.

**Blood samples:** Lithium heparin samples and PAXgene tubes will be transferred to the [name] laboratory at Imperial College London within 4 hours of collection. Serum will be separated from clotted blood following centrifugation, aliquoted and stored at -80°C until transfer on dry ice to the Influenza Laboratory, Public Health England (PHE Colindale) for further analysis.

Documentation included will identify the child by subject number and will allow documentation and tracking of the movement of samples between sites and laboratories (ref study SOPs). Logs of samples sent and received will be kept at PHE Colindale, to enable the identification of any lost or delayed samples and to provide a log of where samples are currently stored.

## 6.4 LABORATORY ASSAYS

### Nasal swabs for Immunoglobulin-A analysis

Immunoglobulin-A will be eluted from the pre-vaccine (and where taken in the sub-study, post vaccine) nasal swabs according to local SOP and analysed for anti-Influenza IgA responses by ELISA. The laboratory has developed a high sensitivity assay for the detection of anti-influenza IgA on flocked swabs. These procedures will take place in [name] GCLP-certified laboratory at the Section of Virology, Imperial College London.

### Oral fluid

All oral fluid samples will be analysed by ELISA using plates coated with antigens specific for the viruses in the vaccine. This will initially be limited to detection of IgG antibody to A/California/7/2009 (antigenically similar to A/Michigan/45/2015 (H1N1)pdm09-like virus, and include detection of antibody specific for H3N2 virus antigenically like the A/Hong Kong/4801/2014 (H3N2)-like virus, B/Brisbane/60/2008-like virus and a B/Phuket/3073/2013-like virus, once these tests have been developed and validated). The method uses the recombinant HA1 fragment of haemagglutinin from each individual vaccine virus for coating 96 well plates, onto which strain specific antibodies, present in oral fluid samples bind. This bound antibody is initially complexed with biotin-labelled anti-human IgG, followed by its detection using streptavidin-HRP conjugate to enhance detection. Each oral fluid is analysed in triplicate in 1:50 dilution. The results will be reported as T/N ratio (OD sample/OD negative control).

## Serological analysis

Analysis of serum samples will be for the presence of haemagglutination inhibition titres to relevant influenza strains (HAI) or Microneutralisation titres according to previously published methods and SOPs, and in compliance with MHRA requirements for GLP.

### Haemagglutination inhibition (HAI)

The principle of the HAI test is based on the ability of specific anti-influenza antibodies to inhibit haemagglutination of red blood cells (RBC) by influenza virus HA. Antibody to influenza virus haemagglutinin has been traditionally associated with protection. Historic studies and recent meta-analyses, indicate that influenza infections are significantly reduced in persons who had preexposure haemagglutination-inhibition (HAI) antibody titres >32 or 40.

The sera to be tested have to be previously treated to eliminate the non-specific inhibitors and the anti-species HAIs found in normal human serum. The HAI experiments, including serum pre-treatment, will be performed in accordance to protocols and SOP's established by RVU. Each serum sample is titrated in duplicate with each virus and individual titres will be reported (two for each sample in each analysis).

### Microneutralisation (MN)

The Microneutralisation assay will only be performed for the analysis of serological responses to the pandemic H1N1 and H7N9 strains. Protocols have already been set up by the laboratory and various previous data indicate that this assay is more sensitive (i.e. detects more 4-fold increases and generally higher GMTs) than the HAI. However, MN is not routinely used for analysis of seasonal vaccines for several reasons: There is no defined correlate of protection for the MN, whereas such values are defined for HAI and SRH. Secondly, this test is technically more demanding and time consuming than the HAI. Lastly, the cross-reactivity between strains of currently circulating (seasonal) viruses and resulting pre-existing immunity complicates the development of specific and sensitive MN protocols and potentially confuses interpretation of results from vaccine trials.

The Microneutralisation assays for measurement of responses to the A(H1N1)pdm09 component of the LAIV and cross-reactive responses to unrelated subtypes (such as H7N9), including serum pre-treatment, will be performed in 96- well format according to previously described protocols and SOPs developed at RVU. The Microneutralisation analysis will be performed in duplicate (in separate runs on 2 days) for each sample and both titres will be reported for each sample.

### Cell Mediated Immunity (CMI)

The T-cell response to influenza virus will be assessed by Fluorescence-immunospot that will quantify the magnitude of cross-reactive IFN $\gamma$  and IL-2 secreting T-cells. Where sufficient cells remain, detailed characterisation of the protective phenotype of cells will be undertaken using flow-cytometry to identify the induction and maintenance of protection-associated CD8+ T-cells.

